**Table 12: Analysis Sets** 

Analysis Set	Description of Population	Reference
Full Analysis Set*	
 
Received any study treatment (at least 1 complete or partial dose)
 
	ICH E9 (5.2.1)
Per Protocol Set	Met all eligibility criteria	ICH E9 (5.2.2)
	Have received all study treatments per protocol	
	
 
Underwent DWEK/DSO of 4 to 5mm
 
	
	
 
Have sufficient data collected for the accurate assessment of study endpoints
 
	

\*The Full Analysis Set will be used for the Safety Population

The Per Protocol Population will be used to assess the primary and secondary efficacy endpoints compared to the control group.

The Safety Population set includes all participants in participants who received any TTHX1114 and will be the population for safety outcomes; this population will be compared with the control group. Ocular AEs involving the study eye will be tabulated. Ocular AEs for the fellow eye and non-ocular AEs will be provided as a listing.

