# 5.3 Subject Withdrawal Criteria

Subjects will be discontinued from continued study treatment if any of the following occur:

- Intolerable side effects
- The Investigator feels it is in the subject's best interest
- Non-compliance
- Pregnancy

Subjects who are discontinued from study treatment are expected to remain on the study and complete all appropriate safety and efficacy assessments.

Subjects may withdraw from the trial at any time and for any reason.

If a subject withdraws from the trial, attempts should be made to contact the subject to determine the reason(s) for discontinuation while respecting the subject's privacy. All procedures and evaluations required by the final study visit should be completed in the event of early withdrawal. All subjects who discontinue the trial due to an adverse event must be followed until the event has resolved, returned to baseline, or stabilized (if resolution is not anticipated).

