# 6.2.2 Subsequent TTHX1114 Administrations

Following the Day 0 TTHX1114 administration, subsequent weekly administrations will occur approximately every 7 days  $\pm 1$  day. If a study treatment administration cannot be administered within the 6 to 8 days following the prior administration, the study treatment may be delayed, and the scheduling of all remaining administrations adjusted to ensure that TTHX1114 is not administered fewer than 5 days after the prior administration.

Confidential and Proprietary

Amendment 7.0: September 22, 2022

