### 6.5.2 On-study Visits

The frequency of on-study visits will vary depending on the treatment group to which the study subject belongs.

All study drug administration dates must be at least 5 days after the prior study drug administration day (if applicable). All other visits will be scheduled based on the number of days since Day 0. If a study drug administration cannot be administered within the protocol window, it should be administered as soon as practicable.

Worksheets will be provided describing which assessments are required at each visit for each treatment group.

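### The visible protocol assigns efficacy to a Per Protocol Set that drops subjects who stop injections although their Day 28 results are collected, so within-group Day 28 rates can be biased in either direction

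*Combined protocol and SAP*

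**What the plan says.** Table 12 in Section 9.3.1 defines two sets. The Full Analysis Set holds everyone who received at least part of one dose. The Per Protocol Set adds conditions, among them "Have received all study treatments per protocol", a descemetorhexis of 4 to 5 mm, and "Have sufficient data collected for the accurate assessment of study endpoints". The last of these is not defined further.

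The text below the table assigns efficacy: "The Per Protocol Population will be used to assess the primary and secondary efficacy endpoints compared to the control group". The only use given to the larger set is in the footnote: "The Full Analysis Set will be used for the Safety Population". Section 9.3.1 describes the Full Analysis Set as aiming at the intention-to-treat ideal, but attaches no efficacy analysis to it.

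Section 5.3 lists the grounds for stopping injections: intolerable side effects, non-compliance, pregnancy, and "The Investigator feels it is in the subject's best interest". It then says: "Subjects who are discontinued from study treatment are expected to remain on the study and complete all appropriate safety and efficacy assessments".

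On late injections, Section 6.2.2 says that "the study treatment may be delayed, and the scheduling of all remaining administrations adjusted", and Section 6.5.2 says "If a study drug administration cannot be administered within the protocol window, it should be administered as soon as practicable". Table 12 does not say whether an injection given late under these rules still meets the Per Protocol condition.

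Section 4.1 counts, by group, subjects with BCVA of 20/40 or better at Day 28. Section 7 makes Day 28 the primary timepoint.

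**The concern.** A subject who stops injections because of intolerance or at the Investigator's judgement still has a Day 28 assessment, but fails the Per Protocol condition on its plain reading. The result is collected and then omitted. Intolerance and Investigator judgement can both be linked to how the eye is doing, so the subjects who remain need not represent the group that was treated.

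The opportunity for this differs by group. Groups 2 and 4 have three post-operative injections before Day 28 (Days 7, 14 and 21). Group 3 has one injection, at surgery, and none afterwards.

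Section 9.2 plans a comparison with the untreated control, but Table 7 shows Group 1 closed after one subject. Readers will therefore rely on each group's own Day 28 rate, which is what this selection can distort. The study is described as giving a preliminary estimate, so what is at stake is a misleading estimate rather than a false formal test.

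**Working it through.** **The plan's own figures.** Section 9.1 gives 16 active and 8 control subjects on practical grounds, with no alpha, power, effect size or response rate, so there is no statistical calculation to reproduce. The Table 7 total does check: using the closed counts for Groups 1 and 2, 1 + 9 + 20 + 20 = 50, which agrees with up to 50.

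**Post-operative injections before Day 28** (Table 7 and the group descriptions in Section 4):

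| Group | Subjects in Table 7 | Post-operative injections |
|---|---|---|
| 1 | 1 (closed) | 0 |
| 2 | 9 (closed) | 3 |
| 3 | 20 | 0 |
| 4 | 20 | 3 |

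Injections on Day -3 (Group 2) and Day 0 are not counted, since both precede any post-operative course. The optional fifth injection in Group 4 is also not counted.

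**Whole-subject illustration.** The response counts are assumed; no stopping rate is needed.

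- Start from 12 of 20 = 60.0%. The exact (Clopper-Pearson) 95% interval is about 36% to 81%.
- Drop two non-responders: 12/18 = 66.7%.
- Drop two responders: 10/18 = 55.6%.
- In Group 2, start from 5 of 9 = 55.6%. Dropping one non-responder gives 5/8 = 62.5%; dropping one responder gives 4/8 = 50.0%.

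**Stopping-rate illustration.** Let p be the response rate among all treated subjects and h the chance of stopping at each of the three injections. Take p = 0.60 and h = 0.05, both assumed.

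- Share who stop at some point: d = 1 - (1 - h)^3 = 1 - 0.95^3 = 0.143.
- If stoppers respond half as often (30%): (p - d × 0.5p)/(1 - d) = (0.600 - 0.143 × 0.300)/0.857 = 65.0%.
- If stopping is unrelated to response, the rate stays at 60%.
- If only responders skip: p(1 - d)/[p(1 - d) + (1 - p)] = 0.514/(0.514 + 0.400) = 56.3%, with 0.60 × 0.143 = 8.6% of the group removed.

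**Range over the assumed h, with p = 0.60:**

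| h per injection | Stoppers respond half as often | Only responders skip |
|---|---|---|
| 2% | 61.9% (+1.9 points) | 58.5% (-1.5) |
| 5% | 65.0% (+5.0) | 56.3% (-3.7) |
| 10% | 71.2% (+11.2) | 52.2% (-7.8) |

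The 10% row is extreme: d = 27.1%, so in the upward case over a quarter of the group would be removed. With p = 0.50 and h = 5%, the two results are 54.2% and 46.2%. A group with no post-operative injections keeps its rate unchanged in every row.

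**The case against.** The strongest reply is that the full analysis is deferred. Section 9.3 says an SAP will be written before database lock, and the amendment history records that endpoint definitions were aligned with one, so some version existed. The abbreviation list includes ITT, LOCF and MMRM, which the visible analysis text never uses. A reader might infer that the trial has no all-treated efficacy analysis at all. The documents do not support that; the point holds for the visible protocol.

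It can also be said that the Per Protocol sentence covers only the comparison with control, and that Sections 4.1 and 9.2 name no set for group rates. That ambiguity is real. But no other set is named for efficacy anywhere, so the stated rule is the only one a reader can follow.

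Other stronger readings are tempting and should be resisted:

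- **That this biases a planned comparison of Group 3 with Group 4.** No such comparison is planned. Subjects go to whichever group is open, depending also on whether they wish to receive drug (Sections 4 and 4.2). Contrasts between regimens are non-comparative in any analysis set.
- **That the bias must favour the drug.** Recovered eyes that skip injections would push the rate down. Recovery is not a listed ground for stopping, so that route needs Investigator judgement or non-compliance, but it is not excluded.
- **That responders might also miss the Day 0 dose.** That dose is given at surgery, before any response exists.
- **That checking descemetorhexis size particularly in slow-healing eyes biases the size exclusion.** Section 6.1.1 asks for at least one post-operative scan in general; if that is followed, the effect is nil.

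Finally, the illustrated shifts are small beside the sampling error in 20 subjects. That is correct, but imprecision is no reason to add an avoidable selection.

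**Conclusion.** The point stands for the visible protocol. The stated rule omits collected Day 28 results from subjects who stop injections, for reasons that can be linked to outcome. It can act at three post-operative injections in Groups 2 and 4 and at none in Group 3. Within-group Day 28 rates can therefore be biased up or down, or not at all if stopping is unrelated to response.

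The size cannot be established from the documents. At the assumed 60% response and 5% stopping per injection, the shift is between -3.7 and +5.0 points, depending on who stops. How many subjects are affected also depends on whether a delayed injection counts as received per protocol, which the protocol leaves open. The change is worth making because it is cheap and removes the selection due to stopped or delayed injections, not because a large bias has been shown.

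**What to change.** 1. Add to Table 12 an efficacy set of all study eyes that underwent DWEK/DSO, analysed by assigned group. Include the Group 1 subject, whom the Full Analysis Set omits because no dose was given, and subjects who stopped or delayed injections. Make this the main efficacy analysis.
2. Keep Per Protocol as a sensitivity analysis, listing the number of exclusions and the reason for each by group.
3. Before database lock, state whether an injection delayed under Section 6.2.2 or 6.5.2 counts as received per protocol for this set.
4. Reconcile the size wording: Section 6.1.1 excludes eyes over 5 mm from efficacy analyses, while Table 12 requires 4 to 5 mm, so eyes under 4 mm fail Table 12 but are not named in the Section 6.1.1 exclusion. The exclusion of eyes over 5 mm was a deliberate amendment and may stand, with results including those eyes shown alongside.

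The cost is wording in Table 12, Section 6.1.1 and the SAP. No extra visits are needed, because stopped subjects are already expected to complete efficacy assessments. The downside is that the headline rate may shift by a few points and protocol departures will dilute the regimen effect; the Per Protocol result remains available for that question. If the SAP already contains an all-treated efficacy analysis, what remains is to bring the protocol into line and settle items 3 and 4.

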#### 4. TRIAL DESIGN

This is an open-label, multi-center study in which up to approximately 50 subjects with FECD who are scheduled for DWEK/DSO will be enrolled. Study subjects will be assigned to Study Treatment Group based on the Group(s) open at the time of treatment of the primary (first) eye; if a subject elects to have an eligible second (contralateral) eye treated, that "fellow" eye will be treated based on the Group(s) open at the time. The number of subjects per group in the study and per study treatment is summarized below in Table 7.

Amendment 7.0: September 22, 2022

Note: the study was amended to allow treatment of the contralateral eye. To avoid ambiguity the eye that was treated first will be referred to as the Study Eye (SE); the contralateral eye will be referred to as the Fellow Eye (FE).

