#### 6.1.2 The Study Eye (SE)

The Study Eye (SE) will be determined by the Investigator prior to the clinical trial as eligibility for the study required a planned DWEK/DSO procedure planned for the medical management of the patient. The SE is defined as the eye that was selected by the treating physician for surgical intervention of DWEK/DSO and the eye to which TTHX1114 is administered (if applicable).

If a study subject wishes to undergo DWEK/DSO in the Fellow Eye after the SE has recovered, the subject may be re-enrolled in Group 3 or Group 4 and the contralateral eye may be treated. "Recovery" is based on the Investigator discretion following the primary efficacy endpoint evaluation on Day 28 (e.g., BCVA of at least 20/40 or have a measured CCT of less than a 10% increase from baseline). Planned treatment of all contralateral eyes must be discussed with and approved by the Sponsor (or designee) prior to treatment.

[figure not shown]

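### The Study Eye and Fellow Eye labels conflict, so ocular adverse events in a treated second eye may or may not enter the ocular AE percentage

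*Combined protocol and SAP*

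**What the plan says.** Section 4 (Trial Design) lets a subject have the second eye treated on study; that "eye will be treated based on the Group(s) open at the time". A note to the same section then fixes the vocabulary for this situation: "the eye that was treated first will be referred to as the Study Eye (SE"), and "the contralateral eye will be referred to as the Fellow Eye (FE"). The labels follow the order of treatment, and nothing there changes the label once the second eye is itself treated.

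Section 6.1.2 describes the route: "If a study subject wishes to undergo DWEK/DSO in the Fellow Eye after the SE has recovered", then "the subject may be re-enrolled in Group 3 or Group 4 and the contralateral eye may be treated". Both groups receive TTHX1114 (Table 7). The same section also defines the Study Eye (SE) as the eye chosen for DWEK/DSO and "the eye to which TTHX1114 is administered (if applicable"). In the Group 3 and Group 4 schedules (Tables 3 and 4), the row for the intracameral injection is marked SE.

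Section 9.2 summarises ocular AEs in the study eye as the number and percentage of subjects with any such event. Section 9.3.1, below Table 12, says that study-eye ocular AEs are tabulated and that "Ocular AEs for the fellow eye and non-ocular AEs will be provided as a listing". Neither section makes an exception for a fellow eye that had surgery and study drug.

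**The concern.** Safety is part of the primary objective (Section 3), and the Safety Population is defined by receipt of any TTHX1114 (Section 9.3.1). A reader will take the ocular AE percentage as the summary of what happened in eyes exposed to the procedure and the drug. If the Section 4 labels govern Section 9, an event in an injected second eye is handled like a non-ocular event: it appears in a listing and in no count. If the Section 6.1.2 definition governs, the same event is counted. Two analysts could follow the protocol faithfully and produce different safety tables from the same data.

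**Working it through.** **Step 1. The passages side by side, for a second eye re-enrolled in Group 3 or 4**

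| Source | Label for that eye | Its ocular AEs under Sections 9.2 and 9.3.1 |
|---|---|---|
| Section 4, note on labels | Fellow Eye | Listing only |
| Section 6.1.2, definition | Study Eye | Counted and tabulated |
| Section 6.1.2, re-enrolment paragraph | Fellow Eye | Listing only |
| Tables 3 and 4, injection row | SE | Counted and tabulated |

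Section 6.1.2 therefore conflicts with Section 4 and also with itself. Section 9.3.1 writes fellow eye in lower case, but this does not restrict it to an untreated eye: Section 4 uses the lower-case word for a second eye that is to be treated.

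**Step 2. How many second eyes?**

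The documents give no number. Each case needs sponsor agreement: "Planned treatment of all contralateral eyes must be discussed with and approved by the Sponsor (or designee) prior to treatment". Section 5 also caps cumulative TTHX1114 administrations at 5 per subject. That rule stands among those for former TTHX-001 participants but is worded for every subject. Planned administrations, first eye plus second eye, against that cap:

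- Group 3 then Group 3: 1 + 1 = 2
- Group 3 then Group 4: 1 + 4 = 5
- Group 4 (four doses) then Group 3: 4 + 1 = 5
- Group 4 then Group 4: 4 + 4 = 8, over the cap
- Full Group 2 course then Group 3: 5 + 1 = 6, over the cap

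So some sequences fit the stated cap and others do not. The number may be small, but the plan does not make it zero.

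**Step 3. Illustration of the effect on the reported figure**

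There is no protocol figure to reproduce for this effect. As a check on the inputs, Table 7 gives 1 + 9 + 20 + 20 = 50, which matches its stated maximum. The TTHX1114 groups give N = 9 + 20 + 20 = 49.

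Assumptions: all 49 are different subjects with an injected first eye; m of them also have an injected second eye; each injected eye has the same AE risk p, independently of the other eye. Neither m nor p is in the documents.

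- Study eye only: percentage = p
- Every injected eye: percentage = [(N − m)p + m(1 − (1 − p)²)] / N = p + m·p(1 − p)/N

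For p = 20%:

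- m = 5: (44 × 0.20 + 5 × 0.36)/49 = 10.6/49 = 21.6%, up 1.6 percentage points
- m = 10: (39 × 0.20 + 10 × 0.36)/49 = 11.4/49 = 23.3%, up 3.3 points

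Other risks, by the same formula:

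| p (study eye only) | m = 5 | m = 10 |
|---|---|---|
| 10% | 10.9% | 11.8% |
| 20% | 21.6% | 23.3% |
| 30% | 32.1% | 34.3% |

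Independence is unfavourable to the plan. Positive correlation between a subject's eyes shrinks the shift; if the two eyes always agreed, the figure would stay at p.

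If the second eyes instead use up Group 3 and 4 places, there are fewer distinct subjects. At p = 20%, m = 5 gives 0.20 + 5 × 0.16/44 = 21.8%, and m = 10 gives 0.20 + 10 × 0.16/39 = 24.1%.

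**The case against.** The strongest reply is that the second eye becomes a study eye on re-enrolment. Section 6.1.2 has the subject re-enrolled in Group 3 or 4. Section 6.1.3 requires registration and treatment group assignment, with a checklist that records earlier participation in this same study. The schedules that then apply mark the injected eye SE. This is a reasonable reading, and it is why omission cannot be asserted outright. But no passage says that re-enrolment changes the label, and the one note written to avoid ambiguity about two treated eyes ties the label to treatment order.

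A second reply is that Section 9.3 promises a full statistical analysis plan (SAP) before database lock, and the document history mentions one. Such a plan could settle the matter. The text available does not, and a SAP author would start from the conflicting definitions.

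A third is that the regimen for counting is obvious, since Sections 4, 6.1.2 and 6.1.3 assign the second eye to a group. That is fair: the natural attribution exists and only an explicit AE-counting rule is missing.

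A fourth is that no event is lost. This stands. Section 4.2 records all AEs, and Section 9.3.1 lists those in the fellow eye. In an open-label study of up to 50 subjects, a reader of the listing can find each one.

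**Conclusion.** The label conflict is certain. Omission from the ocular AE percentage follows only if Section 9 uses the Section 4 labels; under the Section 6.1.2 definition and Tables 3 and 4 there is none. This is worth correcting because one stated rule gives an incomplete summary for part of the primary objective.

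Three stronger readings are tempting, and the documents do not support them:

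- A reader might infer that the plan definitely excludes treated second eyes. The passages point both ways.
- A reader might infer that safety data are discarded. They are recorded and listed.
- A reader might measure the problem as the share of injected eyes left out, for example 5/(49 + 5) = 9.3% or 10/(49 + 10) = 16.9%, or a larger share within Groups 3 and 4. Section 9.2 reports a percentage of subjects, so such shares do not measure the distortion, and Sections 9.2 and 9.3.1 do not specify AE rows by Group 3 or 4.

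The actual size is unknown. With the assumed 20% independent per-eye risk and 49 distinct subjects, the shift is about 1.6 points for 5 second eyes and 3.3 points for 10, and smaller under positive correlation. These figures show scale only.

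**What to change.** Give a treated second eye one label, used identically in Section 4, Section 6.1.2, the schedules of events and Section 9.

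In Sections 9.2 and 9.3.1 and in the SAP, tabulate ocular AEs for every eye that had DWEK/DSO on study or received TTHX1114, attributed to the regimen that eye received. Name the Group 1 control eye explicitly, since it receives no TTHX1114 and would be lost from a rule based on injection alone. Keep the percentage of subjects as the main figure and place a count per treated eye beside it. Keep listing-only for untreated fellow eyes. Check any existing SAP draft for this point first.

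The cost is wording and one extra table; no new data are needed. The drawback is that two eyes of one subject are correlated, so a per-eye percentage must be read with that in mind and not as if the eyes were independent subjects.

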### 10. QUALITY CONTROL AND QUALITY ASSURANCE

#### **10.1** Data Quality Assurance

This study will be conducted and monitored in accordance with GCP and the Study Monitoring Plan (SMP).

#### 10.1.1 Monitoring

Monitoring of this study will include onsite and remote data review and verification. Site monitors will review CRFs to ensure that the collected data accurately reflects the individual subject's experience. Site monitors will also monitor protocol compliance. Protocol deviations include any departure from the study protocol whether intentional or inadvertent. The Medical Monitor (or designee) will periodically review all deviations and determine is corrective action (e.g., investigational site staff retraining) is required. Important deviations will include subjects who:

Were enrolled and did not satisfy the entry criteria

Confidential and Proprietary

Amendment 7.0: September 22, 2022

- Developed withdrawal criteria during the study but were not withdrawn
- Received the wrong treatment or incorrect dose or an excluded concomitant

Important protocol deviations will be reported to the Medical Monitor(s) in an expedited manner.

# 10.1.2 Database Management and Quality Control

Reported data will be systematically reviewed and monitored throughout the study. Review will include an assessment of completeness and quality of data. A subset of data variables in the database and CRFs will be source data verified using a risk-based approach. Trefoil (or designee) will issue data queries and/or request for clarification to the investigational site staff as needed. Additional investigational site training will be provided as needed.

